7.1.5 Admission to Clinical Research Unit (Day 14)

In the evening before the dosing day, subjects will be admitted to the CRU at least 12 hours prior to Day 15 dosing for an overnight fast. Subjects will refrain from all food and drinks except water from the evening after dinner of Day 14. They will have fasted for at least 10 hours at the time of drug administration (fasting cohort) or standard breakfast (fed cohort) next morning (see Section 6.6).

Trial eligibility assessments will include: physical examination, vital signs (blood pressure, pulse rate, temperature and respiration), ECG, and concomitant medications (Table 1). Testing for drug

abuse will be performed. In addition, a blood sample for determination of hematology and biochemistry will be taken and a urinalysis will be performed.

If the subject is determined to be ineligible for any of the above assessments, the subject will be dismissed from the CRU and will not continue with the trial.

Any AEs will be collected and recorded on the eCRF.

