EMR200006-001

Bisoprolol & Amlodipine

Schedule of Assessments

Table 1

Assessments ^a	Scr	Screening				Peri	Period 1								Ь	Period 2	12				End of Trial	End Prematur of Withdra
	-7 ~ -2	-1 Admission	1 ^b	2 3	3 4	5	9	7	8 Discharge	9-13	14 Admission	15 ^b	16	17	18	19	20	21 1	22 Discharge	23-28	29	
Informed consent form signed	X																					
Demographic information	X				2																	
Inclusion/exclusion criteria	X																					
History of alcohol and nicotine consumption	X														Y 7							
Medical history	X			Н																		
Prior medications	Xc																					
Laboratory tests	X								X		X								X			X
Serum Pregnancy test (only for females of child-bearing potential)	×				Į.				x										х			X
HIV antibody, HBsAg, HCV antibody, and TP antibody tests	×				, ,																	
Urine screening of drugs of abuse and breath test of alcohol	×	Х									х											
Urine nicotine	X																					
Randomization			X																			
Drug administration			X									X										
Blood sampling for Pharmacokinetics ^d			×	×	×	×	×	×	×			×	X	×	×	×	×	×	×		×	×
													l			l						

Bioequivalence Trial of Concor AM® vs Bisoprolol and Amlodipine in Chinese Subjects Bisoprolol & Amlodipine

EMR200006-001

Assessments ^a	Scr	Screening				Pel	Period 1	-								Period 2	d 2				End of Trial	End Prematur of Withdra wal
Day	-7 ~ -2	-7 ~ -2 Admission	1 ^b 2		3	3 4 5 6 7	9	7	8 Discharge 9-13 A	9-13	14 Admission 15 ^b 16 17 18 19 20 21	15 ^b	16	17	18	19	20	21	22 Discharge	23-28	29	
Physical examination	X	X							X		X								X			X
Vital signs (blood pressure, pulse rate, temperature and respiration) ^e	X	Х	хх		X	₩.	X	2000	x		Х	×	×	×	×		×		Х			×
Electrocardiogram ^f	X	X	X	NG	X				X		X	X		X					X			X
Chest X-ray	X			Н					X										X			X
AEs and concomitant therapies [§]											Continuous	STI										

AE = adverse event; HBsAg = hepatitis B surface antigen; HCV = hepatitis C virus; HIV = human immunodeficiency virus; TP = treponema pallidum

Subject will participate in the clinical trial on an in-house basis during Day -1 to Day 8 and also during Days 14 to 22. Subjects are excused from the clinic during certain days after each period: from trial Day 9 to Day 13 and from trial Day 23 to Day 28.

After the single dose administration, Washout begins.

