6.2 Dosage and Administration

Potential trial subjects will be examined at a screening examination to determine their eligibility for participation. These tests are to be conducted within 7 days before the first trial administration (Day 1, Period 1).

On the evening before the dosing day in each period, subjects will be admitted to the CRU to fast prior to Day 1 dosing (administered the next morning). During the fast, subjects will refrain from all food and drinks except water from the evening after dinner of Day -1. Water will be provided until 2 hours predose; the drug will be given with 240 mL (8 ounces) of water at room temperature; water will then be allowed *ad libitum* beginning 1 hour after the administration of the drug.

- The subjects in the fasting cohort will have fasted for at least 10 hours by the time of predose blood sample collected after 07:00 on the first day of each period.
- For the fed cohort, subjects will consume a standard breakfast started from 30 minutes before dosing and finished by 10 minutes before dosing. The single dose of trial drug administration will occur 10 minutes after breakfast completion around 07:00 in the morning of the first day of each period. The content of the breakfast will match the high-fat, high-calorie recommendation based on the regulatory guideline.

All subjects will be required to refrain from drinking water during the first 1 hour after drug administration and to refrain from eating during the first 4 hours. Standard diet for lunch and dinner will be served for both fasting and fed cohorts. Beverages should be controlled: fluid intake will be controlled for each in-house period for all subjects. The subjects should drink at least 2 L of water during the first 24 hours after drug administration.

On Day 1 before first trial drug administration, ECG and vital signs will be assessed. If the subject does not meet all eligibility requirements, the subject cannot be randomized to the trial.

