Electrocardiogram Recording

A 12-lead ECG (including QTc evaluation) will be performed.

Results of the ECG recordings will be included in the subject's eCRF. Printouts for each ECG will include date, time, initials of the technician/nurse, and initials of the Investigator who reviewed the printout. At least 5 to 7 beats will be monitored at a speed of 25 mm/sec for each lead and a single lead (V2) run (see Section 7.3.4 for specific ECG determinations and procedures).

Chest X-ray

A chest X-ray examination will be performed.

Laboratory Tests

Hematology assessments

Parameter	Dimension/Unit
Erythrocytes	×10 ¹² /L
Hemoglobin	g/L
Hematocrit	%
Mean corpuscular volume	fL
Mean corpuscular hemoglobin	pg
Mean corpuscular hemoglobin concentration	g/L
Red blood cell distribution width	%
Platelets	×10 ⁹ /L
Mean platelet volume	fL
Thrombocytocrit	%
Platelet distribution width	%
White blood cells	×10 ⁹ /L

Hematology assessments for differential white blood cell counts

Parameter	Dimension/Unit
Neutrophils	10 ⁹ /L and %
Monocytes	10 ⁹ /L and %
Lymphocytes	10 ⁹ /L and %

Biochemistry assessments

Parameter	Dimension/Unit
Alanine aminotransferase	IU/L
Aspartate aminotransferase	IU/L
Total bilirubin	μmol/L
Direct bilirubin	μmol/L
Indirect bilirubin	μmol/L
Protein total	g/L
Albumin	g/L
Globulin	g/L
A/G	(Not applicable)
Alkaline phosphatase	IU/L
Glutamyl transpeptidase	IU/L
Urea nitrogen	mmol/L
Creatinine	μmol/L
Cholesterol	mmol/L
Triglycerides	mmol/L
Glucose	mmol/L
Creatine kinase	IU/L
Lactate dehydrogenase	IU/L
Calcium	mmol/L
Phosphorus	mmol/L
α-Amylase	U/L
Sodium	mmol/L
Potassium	mmol/L
Chloride	mmol/L

Note: If creatine kinase is above the upper limit of normal and evaluated as clinically relevant, a retest should be done and the creatine phosphokinase MB isoenzyme should be determined.

Urinalysis

Appearance, blood, glucose, ketones, nitrite, pH, protein, and leukocytes will be assessed. Microscopic examination will only be performed if dipstick test is positive for leukocytes, blood, nitrites, or proteins.

Serum pregnancy test

Pregnancy testing for females of childbearing potential only (Human Chorionic Gonadotropin in serum)

Other laboratory tests

Serology

HIV antibody

HBsAg

HCV antibody

TP antibody

Urine screening of drugs of abuse

The following urine tests for drug abuse will be conducted: levels for other drugs of abuse (eg, cannabis, benzodiazepines, barbiturates, opiates, cocaine, and methyl amphetamine).

Breath test of alcohol

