7.1.2 Admission to Clinical Research Unit (Day -1)

In the evening before the dosing day, subjects will be admitted in an in-house status to the CRU at least 12 hours prior to Day 1 dosing for an overnight fast. Subjects will refrain from all food and drinks except water from the evening after dinner of Day -1. They will have fasted for at least 10 hours by the time of drug administration (fasting cohort) or standard breakfast (fed cohort) next morning (see Section 6.7.3).

Trial eligibility assessments will be performed including: physical examination, vital signs, ECG and concomitant medications, treatments and diseases as well as testing for drug abuse.

If the subject is determined to be ineligible for the trial due to any of the above assessments, the subject will be considered a screening failure and will not continue to randomization to the trial.

Adverse events will be collected and recorded on the eCRF.

7.1.3 **Period 1 (Day 1 to Day 8)**

Day 1, Trial Drug Administration

On Day 1, the following assessments will be conducted and/or collected and recorded on the eCRF.

Trial Eligibility Assessments

Subjects will be assessed for vital signs (blood pressure, pulse rate, temperature and respiration). Blood pressure assessments determine eligibility to be randomized to the trial. The blood pressure (measured in supine position after at least 5 minutes rest) must not be below 100 mmHg and/or 65 mmHg or above 139 mmHg and/or 90 mmHg.

A 12-lead ECG (including QTc evaluation) will be performed.

Any concomitant medications, diseases and treatments should be documented. Concurrent administration of any medication will be prohibited during the trial (Section 6.5).

If the subject is determined to be ineligible for any of the above assessments, the subject will not be randomized to the trial.

Any AEs and serious adverse events (SAEs) should also be recorded.

Randomization

Eligible subjects will then be randomly assigned to one of 2 sequences (Table 2).

Baseline Sampling

Eligible subjects will have their baseline blood sample collected before IMP administration in Period 1.

Trial Drug Administration

As per randomization, each subject will receive a single dose of bisoprolol-amlodipine 5 mg/5 mg (given as 1 tablet of 5 mg/5 mg) or a single dose of 5 mg bisoprolol and 5 mg amlodipine (given as 1 tablet of 5 mg bisoprolol and 1 tablet of 5 mg amlodipine, co-administrated) accordingly.

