At the day of discharge, a blood sample for determination of hematology and biochemistry will be taken and a urinalysis will be performed. Serum pregnancy test will be performed for females of childbearing potential only. Physical examination, ECG, and chest X-ray will be performed.

On the morning of Day 8 in the CRU after the blood sampling collection (168-hour sample), the Investigator will decide whether or not the subject needs to stay for any additional time in the clinic. If there are no safety concerns based on the assessment by the Investigator, the subject will be allowed to leave the CRU.

7.1.4 Washout Period 1

The 2 administrations of trial drug are separated by a washout of 14 days. Washout begins postdose on Day 1 and continues for 14 days.

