7.1.6 Period 2 (Day 15 to Day 22)

Day 15, Trial Drug Administration

Procedures outlined on Day 1 in Period 1 will be repeated on Day 15 for continuing trial eligibility into Period 2 (except for randomization).

Baseline Sampling

Eligible subjects will have their baseline blood sample collected before trial drug administration in Period 2.

Trial Drug Administration

Each subject will receive the trial medication according to the randomization plan (investigational product and comparators).

The single dose of trial drug administration will occur after 07:00 in the morning of Day 15. A total volume of 240 mL water will be consumed with the medication. All subjects will be required to refrain from drinking water during the first 1 hour after drug administration and refrain from eating during the first 4 hours. Standard diet for lunch and dinner will be served. Beverages should be controlled: fluid intake will be controlled for each in-house period for all subjects. The subjects should drink at least 2 L of water during the first 24 hours after drug administration.

Pharmacokinetic Blood Sampling (Postdose)

Blood samples for the determination of bisoprolol and amlodipine will be taken at the specified times: 0.5, 1, 1.5, 2, 3, 4, 6, 8, 10, 12, and 15 hours (Table 3).

Safety Monitoring

Any concomitant diseases and treatments have to be documented. Concurrent administration of any medication will be prohibited during the trial (Section 6.5.1).

Any AEs and SAEs are also to be recorded.

Vital signs (blood pressure, pulse rate, temperature and respiration) will be taken prior to dosing and also at 4, 8, and 12 hours postdose.

A 12-lead ECG (including QTc evaluation) will be performed 4 hours postdose.

Day 16 to Day 22

Pharmacokinetic Blood Sampling (Postdose, continued)

Blood samples for the determination of bisoprolol and amlodipine will be taken at the specified times (Table 3).

On Day 16, sampling will be conducted at 24 and 36 hours; from Day 18 to Day 22, sampling will be conducted every 24 hours. The subject is allowed to leave the CRU on Day 22 after the morning blood sampling (168 hour sample).

Safety Monitoring

Any concomitant diseases and treatments have to be documented. Concurrent administration of any medication will be prohibited during the trial (Section 6.5.1).

Any AEs and SAEs should also be recorded.

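### The Day 15 dose relies on a Day 8 pregnancy test; adding a test to the Day 14 eligibility check would be a cheap improvement with a very small gain

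*Protocol*

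**What the plan says.** **Where the tests are.** Table 1 of the protocol gives the test its own row, "Serum Pregnancy test (only for females of child-bearing potential", marked at Screening, Day 8, Day 22 and Premature Withdrawal. The row has no mark at Day -1, Day 1, Day 14 or Day 15. Section 7.1.3, under the day of discharge from Period 1, confirms the Day 8 test: "Serum pregnancy test will be performed for females of childbearing potential only". Section 7.1.1 defines it as "Human Chorionic Gonadotropin in serum".

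**What happens on Day 14.** Section 7.1.5 lists physical examination, vital signs, ECG and concomitant medications as eligibility assessments and adds drug-abuse testing. It then says: "In addition, a blood sample for determination of hematology and biochemistry will be taken and a urinalysis will be performed". The consequence of failing follows: "If the subject is determined to be ineligible for any of the above assessments, the subject will be dismissed from the CRU".

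**What happens on Day 15.** Section 7.1.6 says: "Procedures outlined on Day 1 in Period 1 will be repeated on Day 15 for continuing trial eligibility into Period 2". The Day 1 procedures in Section 7.1.3 include no pregnancy test.

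**The first dose.** For the screening examination, Section 6.2 says: "These tests are to be conducted within 7 days before the first trial administration (Day 1, Period 1". The Day -1 check in Section 7.1.2 covers "physical examination, vital signs, ECG and concomitant medications, treatments and diseases as well as testing for drug abuse", again without a pregnancy test.

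**Rules on pregnancy.** A positive test is exclusion criterion 23 (Section 5.3.2). Section 7.3.2 requires immediate discontinuation of trial medication if a subject becomes pregnant. Section 6.7.5 requires contraception with a failure rate below 1% per year during treatment and for at least 14 days after the last dose.

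**The concern.** At the second dose the protocol already has what it needs to withhold treatment from a pregnant subject: a visit the evening before, blood and urine collected at that visit, and a dismissal rule. It repeats hematology, biochemistry, urinalysis, physical examination, vital signs and ECG on Day 14, although all were done on Day 8. The pregnancy test is not repeated.

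A pregnancy too early to detect on Day 8 can therefore receive a second dose that Section 7.3.2 would have stopped had the pregnancy been known. Day 15 is the only dose a later test could still prevent, because the Day 22 test comes after it. What is at stake is avoidable fetal exposure in a healthy-volunteer trial. No pharmacokinetic endpoint is involved.

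**Working it through.** **1. Confirm that only one pregnancy test is planned in Period 2.** Section 7.1.1 lists the pregnancy test under laboratory tests, so the Day 14 laboratory mark in Table 1 could be thought to include it. Table 4 settles this.

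- Screening: 4 + 2 + 4 + 4 = 14 mL
- Period 1: 2 + 4 + 4 + 4×20 = 90 mL
- Period 2: 2×2 + 4×2 + 4 + 4×20 = 96 mL
- End of Trial: 4 mL
- Total: 14 + 90 + 96 + 4 = 204 mL, as stated in Table 4

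Period 2 reaches 96 mL with two hematology and biochemistry draws (Days 14 and 22) and one pregnancy test (Day 22). Two tests would give 100 mL.

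**2. Age of the last result at each dose (calendar without Day 0).**

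- Dose 1: the Table 1 screening column runs from Day -7 to Day -2, so the result is 2 to 7 days old on Day 1.
- Dose 2 as planned: 15 − 8 = 7 days.
- Dose 2 with a Day 14 test: 15 − 14 = 1 day.

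**3. Conception days reached.** Let L be the lag in days from conception to a positive test. The documents do not give it. The undetected window before Day 15 is 7 + L days now and 1 + L days with a Day 14 test. The difference is 6 days at any L, provided both tests have the same lag. The window never reaches zero. The table assumes L = 8 to 11 days.

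| L | Latest conception caught on Day 8 | Latest caught on Day 14 | Added days | Of these, before admission is complete (Day -1 or earlier) |
|---|---|---|---|---|
| 8 | Day -1 | Day 6 | Days 1 to 6 | 0 |
| 9 | Day -2 | Day 5 | Day -1 to Day 5 | 1 |
| 10 | Day -3 | Day 4 | Day -2 to Day 4 | 2 |
| 11 | Day -4 | Day 3 | Day -3 to Day 3 | 3 |

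A conception on Day 9 would be reached only if L were 14 − 9 = 5 days or less. At the assumed lags, none of the outpatient Days 9 to 13 is reached.

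**4. Expected pregnancies in the added days, whole trial.** Each gender makes up at least one third of 32 subjects. Since 32/3 = 10.67, there are 11 to 32 − 11 = 21 women. Count all of them as being of childbearing potential and apply 1% per year:

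- 11 × 0.01 × 6/365.25 = 0.0018 (0.18%)
- 21 × 0.01 × 6/365.25 = 0.0034 (0.34%)

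If conception is assumed impossible once subjects are admitted, only 0 to 3 of the 6 days count. The range is then 0 to 21 × 0.01 × 3/365.25 = 0.0017 (0.17%).

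**5. Blood volume with a serum test.** Period 2: 4 + 8 + 8 + 80 = 100 mL. Total: 14 + 90 + 100 + 4 = 208 mL, which is 4/204 = 2.0% more.

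**The case against.** The strongest reply is that this is a preference. The protocol accepts a result up to 7 days old at dose 1 and one exactly 7 days old at dose 2. It also requires contraception, tests at both discharges and follows up any pregnancy. That stands. A reader might infer that dosing on Day 15 without a fresh test contradicts exclusion 23 or Section 7.3.2. It does not: the first acts on a positive test and the second on a pregnancy that has occurred, and neither fixes when to test. A reader might also infer that dose 2 is held to a laxer standard than dose 1, but the intervals are similar.

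The Day 14 blood is also not clearly an eligibility test. Section 7.1.5 introduces it after the eligibility list, and SAP Section 17.2 uses Day 14 as the Period 2 laboratory baseline. Nothing says the results must be read before dosing. This partly stands, and it means the new test would have to be named as an eligibility assessment.

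Timing stands as well. Subjects are admitted about 12 hours before dosing (Section 6.7.3), and no laboratory turnaround is documented.

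Finally, the benefit is tiny. The Day 1 exposure cannot be undone, and with an amlodipine half-life of 35 to 50 hours (Section 3.1), conceptions soon after Day 1 already overlap the first dose. At a lag of 8 days and with conception excluded in-house, the gain is zero. This limits how much weight the point deserves. The change remains reasonable only because it costs so little.

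**Conclusion.** The point holds as an optional, low-cost improvement in subject safety. The schedule facts are firm: the Day 15 dose rests on a 7-day-old result, and a Day 14 test would make that 1 day.

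A reader might infer that the added test would close the gap, or would catch pregnancies beginning in the outpatient washout. The calculation supports neither: the undetected window shrinks by 6 days and remains open.

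The size rests on three assumptions. The lag of 8 to 11 days comes from outside the documents. Counting every woman as being of childbearing potential overstates the number at risk, because the actual share is not given. The 1% per year rate is an assumption, above all before dose 1: Section 6.7.5 states no contraception period before treatment, and Appendix I notes that typical-use failure rates may differ. The figures scale in proportion to the true rate, so they are upper values only if 1% holds. Sample size, power and the bioequivalence comparison are untouched.

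**What to change.** Add a pregnancy test for women of childbearing potential on Day 14 in Table 1, and list it among the eligibility assessments in Section 7.1.5 so that the dismissal rule covers it. Require a negative result before Day 15 dosing. Keep the Day 8 and Day 22 tests.

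- **If a serum result is available overnight:** use the existing draw and amend Table 4 (Period 2 from 96 to 100 mL, total from 204 to 208 mL).
- **If not:** use a rapid test on the urine already collected, with no added blood. If its lag is longer than that of the Day 8 serum test, the gain falls below 6 days by the difference.

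The cost is a short amendment, plus 4 mL of blood or one rapid test per woman tested. No extra visit or venepuncture is needed. Amendment 2.0 cut PK blood, partly on the Ethics Committee's recommendation, from 41 × 5 = 205 mL to 41 × 4 = 164 mL. The serum option gives back 4 of those 41 mL (9.8%), only in the women tested. The real operational demand is having the result before dosing. The dose 1 interval is left as it is.

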7.1.6 Period 2 (Day 15 to Day 22)

Day 15, Trial Drug Administration

Procedures outlined on Day 1 in Period 1 will be repeated on Day 15 for continuing trial eligibility into Period 2 (except for randomization).

Baseline Sampling

Eligible subjects will have their baseline blood sample collected before trial drug administration in Period 2.

Trial Drug Administration

Each subject will receive the trial medication according to the randomization plan (investigational product and comparators).

The single dose of trial drug administration will occur after 07:00 in the morning of Day 15. A total volume of 240 mL water will be consumed with the medication. All subjects will be required to refrain from drinking water during the first 1 hour after drug administration and refrain from eating during the first 4 hours. Standard diet for lunch and dinner will be served. Beverages should be controlled: fluid intake will be controlled for each in-house period for all subjects. The subjects should drink at least 2 L of water during the first 24 hours after drug administration.

Pharmacokinetic Blood Sampling (Postdose)

Blood samples for the determination of bisoprolol and amlodipine will be taken at the specified times: 0.5, 1, 1.5, 2, 3, 4, 6, 8, 10, 12, and 15 hours (Table 3).

Safety Monitoring

Any concomitant diseases and treatments have to be documented. Concurrent administration of any medication will be prohibited during the trial (Section 6.5.1).

Any AEs and SAEs are also to be recorded.

Vital signs (blood pressure, pulse rate, temperature and respiration) will be taken prior to dosing and also at 4, 8, and 12 hours postdose.

A 12-lead ECG (including QTc evaluation) will be performed 4 hours postdose.

Day 16 to Day 22

Pharmacokinetic Blood Sampling (Postdose, continued)

Blood samples for the determination of bisoprolol and amlodipine will be taken at the specified times (Table 3).

On Day 16, sampling will be conducted at 24 and 36 hours; from Day 18 to Day 22, sampling will be conducted every 24 hours. The subject is allowed to leave the CRU on Day 22 after the morning blood sampling (168 hour sample).

Safety Monitoring

Any concomitant diseases and treatments have to be documented. Concurrent administration of any medication will be prohibited during the trial (Section 6.5.1).

Any AEs and SAEs should also be recorded.

Vital signs (blood pressure, pulse rate, temperature and respiration) will be assessed before blood sampling from Day 16 to Day 22.

A 12-lead ECG (including QTc evaluation) will be performed 48 hours postdose at Day 17.

At the day of discharge, a blood sample for determination of hematology and biochemistry will be taken and a urinalysis will be performed. Serum pregnancy test will be performed for females of childbearing potential only. Physical examination, ECG, and chest X-ray will be performed.

On the morning of Day 22 in the clinic after the morning blood sampling collection (168-hour sample), the Investigator will decide whether or not the subject needs to stay for any additional time in the clinic. If there are no safety concerns based on the assessment by the Investigator, the subject will be allowed to leave the clinic.

7.1.7 Washout Period 2

Washout in Period 2 begins postdose on Day 15 and continues for 14 days through Day 28.

